9.3.3 CLIF-C ACLF Score, CLIF-C AD Score

The CLIF-C Acute-on-Chronic Liver Failure (ACLF) score is a continuous numeric value in the range of 0-100 with a higher number representing more severe disease, derived from the CLIF-C OF total score, and is defined as:

$$\text{CLIF-C ACLF} = 10*[0.33*\text{CLIF-C OFs} + 0.04*\text{Age} \{ \text{years} \}^{\#} + 0.63*\text{Ln}(\text{white cell count} \{ 10^9 \text{ cells/L} \}) - 2].$$

The CLIF-C Acute Decompensation (AD) score is a continuous numeric value in the range of 0-100 with a higher number representing more severe disease, and is defined as:

$$\text{CLIF-C AD} = 10*[0.03*\text{Age} \{ \text{years} \}^{\#} + 0.66*\text{Ln}(\text{Creatinine} \{ \text{mg/dL} \}) + 1.71*\text{Ln}(\text{INR}) + 0.88*\text{Ln}(\text{white cell count} \{ 10^9 \text{ cells/L} \}) - 0.05*\text{Sodium} \{ \text{mmol/L} \} + 8].$$

The CLIF-C ACLF and AD scores will be included in the listing of CLIF-C OF scores, and each will be summarized as a continuous variable. The total score and change in total

GRIFOLS	Number	IG1601	Big-CL-SP-000319	Version	2.0	Status	Effective	Effective Date	09-Sep-2024	Page	35 of 52
	IG1601 Statistical Analysis Plan										

score from baseline to each post-baseline scheduled visit will be summarized by treatment and visit. In addition, the MMRM analysis of CLIF-C OF scores will be repeated for change from baseline total scores

Subject age as collected on the demographics eCRF page

9.3.4 MELD Score

The Model for End-stage Liver Disease (MELD) score is a continuous numeric value in the range of 6-40, with a higher number representing more severe disease, and is defined as:

$$\text{MELD} = 9.57 * \text{Ln}(\text{Creatinine } \{ \text{mg/dl} \}) + 3.78 * \text{Ln}(\text{Bilirubin } \{ \text{mg/dl} \}) + 11.2 * \text{Ln}(\text{INR}) + 6.43.$$

MELD scores are evaluated monthly through Month 12 and will be listed. If any of the individual clinical parameters used to derive the MELD score report results <1, the result is imputed to 1, and then used to generate the MELD score.

The MELD score will be summarized as a continuous variable. The MELD total score and change in total score from baseline to each scheduled post-baseline visit will be summarized, as a continuous variable, by treatment and scheduled visit. In addition, the MMRM analysis of CLIF-C OF scores will be repeated for the change from baseline total scores

9.3.5 Child-Pugh Score

The Child-Turcotte-Pugh (Child-Pugh) classification for severity of cirrhosis consists of 5 sub-scores for encephalopathy, ascites, bilirubin, albumin, and INR – each with values of 1, 2 or 3 with a higher number representing more severe disease. Refer to protocol Appendix 3 for details. The Child-Pugh Score is a discrete numeric value in the range of 5 to 15 (inclusive) and is defined as the sum of the five sub-scores. If an individual sub-score is missing, the total score will also be missing.

The Child-Pugh Class is derived from the Child-Pugh Score as follows: Class A = score of 5-6; Class B = score of 7-9; Class C = score of 10-15.

Child-Pugh scores are evaluated monthly through Month 12 and will be listed.

Each Child-Pugh sub-score will be summarized as a categorical variable by treatment and scheduled visit. In addition, each Child-Pugh sub-score will be compared by treatment and scheduled visit using the generalized linear models implemented in SAS GENMOD procedure, in which each Child-Pugh sub-score is modeled by the proportional odds

Number	IG1601 Statistical Analysis Plan		
	Version	2.0	Status
Effective	Effective Date	09-Sep-2024	Page
36 of 52			

cumulative logit model for multinomial data with adjustment for, baseline score, region (Europe or North America), history of hospitalization for acute decompensation of liver cirrhosis (yes or no), treatment, visit and treatment-by-visit interaction as independent variables, and the robust variance estimate for the treatment effect will be estimated based on the independent working correlation structure.

The Child-Pugh Total Score and change in total score from baseline to each scheduled post-baseline visit will be summarized, as a continuous variable, by treatment group and scheduled visit. In addition, the MMRM analysis of CLIF-C OF scores will be repeated for the change from baseline total scores.

The Child-Pugh Class will be summarized as a categorical variable by treatment for each visit.

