2.4.2 Justification for Selection of Doses/Timing of Investigational Products

Preliminary Results of Human Albutein 20% Dose-Finding Study

The current albumin dosage in cirrhosis is based on empiric assumptions on the concept that it mainly acts as a plasma expander. However, albumin has other biological effects unrelated to its oncotic capacity (22).

A Grifols-sponsored clinical study (IG0802) was designed to test the hypothesis that normalization of serum albumin concentration by long-term exogenous albumin administration can be a target to achieve in order to potentiate the beneficial effects related to the oncotic and non-oncotic properties (23). In this open-label study, subjects with decompensated cirrhosis who were prone to develop severe circulatory dysfunction and HRS within a short period of time were treated with a low human albumin dose (1 g/kg body weight every 2 weeks for 12 weeks). Following interim analysis results, which did not demonstrate a change in plasma renin activity (PRA), human albumin was administered at a higher dose with an increased frequency (1.5 g/kg body weight every week for 12 weeks).

To assess dose effectiveness, serum human albumin levels were measured at the end of treatment. Treatment with low-dose human albumin was not sufficient to increase the serum albumin levels above 34 g/L (lower limit of normal). In this treatment group, 2 out of 7 subjects with hypoalbuminemia at the baseline visit had serum human albumin levels within the normal range at end of treatment. In contrast, treatment with high-dose human albumin was sufficient to increase serum human albumin levels to within the normal range. Eight of 8 subjects with hypoalbuminemia at the baseline visit had serum human albumin the normal range. Eight of 8 subjects with hypoalbuminemia at the baseline visit had serum human albumin levels within the normal range.

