Appendix 3 Illness Severity Scores

Criteria to Define Organ Failure (CLIF-C OF Score)

CLIF-Organ Failure score system.				
Sub-score = 1	Sub-score = 2	Sub-score = 3		
Bilirubin <6 mg/dL	$6 \leq Bilirubin < 12 mg/dL$	Bilirubin ≥12 mg/dL		
Creatinine <2 mg/dL	$2 \leq Creatinine < 3.5 mg/dL$	Creatinine ≥3.5 mg/dL or renal replacement		
Grade 0	Grade 1-2	Grade 3-4		
INR <2.0	2.0 ≤ INR <2.5	INR ≥2.5		
MAP ≥70 mm/Hg	MAP <70 mm/Hg	Use of vasopressors		
>300 >357	≤300 - >200 >214- <357	≤200 (#) <214 (#)		
	Sub-score = 1 Bilirubin <6 mg/dL	Sub-score = 1Sub-score = 2Bilirubin <6 mg/dL		

The shaded area describes criteria for diagnosing organ failures; *HE: Hepatic Encephalopathy; # patients enrolled in the study with MV were considered as presenting respiratory failure (respiratory sub-score=3) except for patients intubated due to severe HE or to other reasons and not to a respiratory failure, in whom respiratory failure is defined according to the PaO2/FiO2 ratio.

CLIF-C ACLF Score

CLIF-C ACLFs = $10*[0.33*CLIF-C OFs + 0.04*Age {years} + 0.63*Ln(white cell count {10⁹ cells/L}) - 2]$

CLIF-C AD Score

CLIF-C ADs= 10[0.03*Age {years} +0.66*Ln(Creatinine {mg/dL})	
+1.71*Ln(INR)+0.88*Ln(white cell count {10 ⁹ cells/L}) - 0.05*Sodium {mmol/L}+	8]

MELD Score

MELD Score = 9.57 Ln(Creatinine {mg/dL}) + 3.78 Ln(Bilirubin {mg/dL}) + 11.2 Ln(INR) + 6.43

Child Pugh Score

Child-Turcotte-Pugh Classification for Severity of Cirrhosis			
		Points*	
	1	2	3
Encephalopathy	None	Grade 1-2	Grade 3-4
		(or precipitant induced)	(or chronic)
Ascites	None	Mild to moderate	Severe
		(diuretic responsive)	(diuretic refractory)
Bilirubin (mg/dL)	<2	2-3	>3
Albumin (g/dL)	>3.5	2.8-3.5	<2.8
INR	<1.7	1.7-2.3	>2.3

*Child-Turcotte-Pugh Class obtained by adding score for each parameter (total points)

Class A = 5 to 6 points (least severe liver disease)

Class B = 7 to 9 points (moderately severe liver disease)

Class C = 10 to 15 points (most severe liver disease)

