9.3 Exploratory Endpoints

The analysis of the exploratory endpoints will be performed for the ITT population. Exploratory endpoint scores and sub scores will be derived using clinical parameter results reported in the central laboratory dataset. For the clinical parameters not included as part of the central laboratory tests, results will be taken from the relevant eCRF pages.

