9.3.2 CLIF-C OF Score and Sub Scores for Organ Function

CLIF-C OF score is evaluated monthly through Month 12 and will be listed.

The CLIF-C OF score system consists of six sub-scores for liver, kidney, brain, coagulation, circulatory, and respiratory organs/systems – each with values of 1, 2 or 3 with a higher number representing more severe disease. Each CLIF-C OF sub-score will be summarized as a categorical variable by treatment for each visit.

The total CLIF-C OF score is a discrete numeric value in the range of 6 to 18 (inclusive) and is defined as the sum of the six organ/system sub-scores. If an individual sub-score is missing, the total score will also be missing. The total CLIF-C OF score and change in total score from baseline to each scheduled post-baseline visit will be summarized, as a continuous variable, by treatment and scheduled visit. In addition, the total score change from baseline of scheduled visits for both treatment groups will be analyzed by MMRM, which includes change in total score from baseline as the dependent variable; treatment, visit, region (Europe or North America) and history of hospitalization for acute decompensation of liver cirrhosis (yes or no), treatment-by-visit interaction, region-by-visit interaction, and history of hospitalization for acute decompensation of liver cirrhosis-by-visit interaction as fixed effects; baseline and baseline-by-visit as covariates; and measures within-subject at each visit as a repeated measure. The model employs an unstructured covariance matrix for the within-subject dependence. If the model fails to converge, the mixed effects model with a compound symmetry correlation structure will be used.

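### The between-arm comparison of the Child-Pugh total includes a serum-albumin item, so infused albumin can lower the score without any change in liver disease

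*SAP*

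**What the plan says.** SAP 9.3.5 describes a score that "consists of 5 sub-scores for encephalopathy, ascites, bilirubin, albumin, and INR". Each item takes the value 1, 2 or 3, higher being worse. The total "is defined as the sum of the five sub-scores", so it runs from 5 to 15, and Class follows from it (A 5–6, B 7–9, C 10–15). What is summarised by arm and visit is "The Child-Pugh Total Score and change in total score from baseline". Beyond that summary, "the MMRM analysis of CLIF-C OF scores will be repeated for the change from baseline total scores". That model, in SAP 9.3.2, has treatment as a fixed effect and includes "history of hospitalization for acute decompensation of liver cirrhosis (yes or no), treatment-by-visit interaction, region-by-visit interaction", so the arms are contrasted over time. Class is only tabulated.

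SAP 9.3 gives the data source: "Exploratory endpoint scores and sub scores will be derived using clinical parameter results reported in the central laboratory dataset". Protocol Appendix 3 scores the albumin row "Albumin (g/dL) >3.5 2.8-3.5 <2.8" as 1, 2 and 3 points respectively.

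Protocol 2.4.1 sets the intervention at 1.5 g/kg of albumin (at most 100 g) every 10 ± 2 days. Protocol 2.4.2 reports from the dose-finding study that "treatment with high-dose human albumin was sufficient to increase serum human albumin levels to within the normal range", in 8 of 8 subjects who began with hypoalbuminemia. That regimen was 1.5 g/kg weekly for 12 weeks. The largest rises were in those with the lowest starting values.

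Neither document removes, fixes or adjusts the albumin item in the arm given albumin, and no total without that item is planned.

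**The concern.** The albumin item is meant to mark severity of cirrhosis. In one arm it also measures what has been infused, so a between-arm difference in the total mixes two things: change in the disease and presence of the product. The direction is predictable, because the artefact favours the Albutein arm.

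The stake is interpretation. SAP Section 2 says the planned analyses will go into regulatory submissions or manuscripts. A nominally significant Child-Pugh difference could be read there as milder liver disease when it came wholly or partly from the albumin item.

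**Working it through.** **Range of the score.** Five items scored 1 to 3 give 5 × 1 = 5 to 5 × 3 = 15. This reproduces the SAP's range, and only with albumin included. Without albumin the range is 4 × 1 = 4 to 4 × 3 = 12.

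**Change per subject from the albumin item alone.** The Appendix 3 cuts are applied with the other four items held fixed. The protocol's lower limit of normal, 34 g/L, equals 3.4 g/dL.

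| Baseline albumin (g/dL) | Later 3.4–3.5 | Later above 3.5 |
|---|---|---|
| below 2.8 (3 points) | 3 → 2: −1 | 3 → 1: −2 |
| 2.8–3.5 (2 points) | 2 → 2: 0 | 2 → 1: −1 |
| above 3.5 (1 point) | not a favourable move | 1 → 1: 0 |

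The favourable artefact is therefore 0 to 2 points. Reaching the normal range is not enough by itself: a subject going from 3.0 to 3.4 g/dL is normalised and scores 2 both times.

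**Change in Class from the albumin item alone.** Let S be the sum of the other four items.
- S = 4: 7 (B) becomes 6 or 5 (A).
- S = 5: 8 or 7 (B) becomes 6 (A).
- S = 7: 10 (C) becomes 9 or 8 (B).
- S = 8: 11 or 10 (C) becomes 9 (B).

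**How readily the comparison would detect a pure artefact.** If, net of controls, a proportion p of subjects lose one point and q lose two, the mean difference is d = p + 2q. For example, d = 0.5 if half lose one point. The chance of two-sided p < 0.05 at one visit, with no effect on the other items, is approximately

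Φ( d / (SD × √(2/n)) − 1.96 ).

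The documents give no d, no SD of change and no number per arm at a visit, so all three are assumptions. At n = 150 per arm and SD = 2.0, the standard error is 2.0 × √(2/150) = 0.231. For d = 0.5 the probability is Φ(0.5/0.231 − 1.96) = Φ(0.205) = 0.58.

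| Assumed d | n = 150, SD 2.0 | Range over n = 100–205, SD 1.5–2.5 |
|---|---|---|
| 0.25 | 0.19 | 0.11–0.39 |
| 0.50 | 0.58 | 0.29–0.92 |
| 0.75 | 0.90 | 0.56 to >0.99 |
| 1.00 | 0.99 | 0.81 to >0.99 |

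These figures show that a moderate artefact would be detectable. They do not show that one of that size will occur.

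**Which albumin sample is used.** Protocol 7.2.1.2.2 places assessments before the infusion but has serum albumin measured after it as well. SAP 9.3.9 takes the pre-infusion value for change in serum albumin. SAP 9.3.5 names no sample. The tie rule in SAP 6.1.5 takes the later of two assessments equally distant from the target day. Applied to two samples on the same day, it could select the post-infusion value and enlarge the artefact. The note in SAP Appendix 4 settles this for Day 1 only.

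**The case against.** **The endpoint is exploratory.** This stands. Child-Pugh is outside the fixed testing sequence of SAP 6.5, and no primary or secondary conclusion can change.

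**The artefact is already visible.** Partly so. SAP 9.3.5 compares each item separately, so a reader can see whether only albumin moved. MELD and the CLIF-C OF, ACLF and AD scores contain no albumin term and are compared by MMRM, and serum albumin is its own endpoint (SAP 9.3.9). None of these gives the Child-Pugh difference that remains once albumin is set aside.

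**The shift may be small.** This stands as to size. The 8-of-8 result came from weekly dosing. In the same study, 1 g/kg every 2 weeks normalised 2 of 7, and this trial's interval lies between the two. The lower limit of normal is below the 3.5 cut. Protocol 4.4.1.2 lets controls receive albumin after paracentesis and for complications, which narrows the contrast. None of this gives reason to expect no shift: Protocol 2.4.2 presents normalisation of serum albumin as a target.

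**Stronger readings a reader might infer.** One is that infusion lowers every treated subject's score. The table of cuts contradicts that. Another is that the trial will report a spurious significant benefit. That needs a mean shift and an SD that the documents do not supply.

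**Conclusion.** The comparison of the five-item total is open to a mechanical bias toward the Albutein arm. This follows from the documents' own definitions and needs no outside figure. The effect is 0 to 2 points per subject, conditional on crossing 2.8 or 3.5 g/dL, and it can change Class without any change in liver disease.

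The average size cannot be fixed from the documents, and the probabilities above rest on assumed inputs. It would be wrong to infer that the trial's efficacy conclusions are compromised or that Class is being tested: the endpoint is exploratory and Class is descriptive. This is a cheap improvement to interpretation.

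**What to change.** In SAP 9.3.5:

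1. Add the same MMRM on change from baseline in an albumin-free total of encephalopathy, ascites, bilirubin and INR (range 4 to 12), treated as missing if any of the four is missing. Base any between-arm claim about disease severity from Child-Pugh on this analysis.
2. Keep the five-item total and Class as planned, since the protocol names the standard score. Add a note to their tables that the albumin item reflects the infused product in the Albutein arm.
3. State that the pre-infusion albumin value enters the score at every visit, and that the tie rule in SAP 6.1.5 does not choose between pre- and post-infusion samples.

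Record the added analysis in SAP Section 12. The cost is some wording, one derived variable and one extra table, all from data already collected. The downside is that the four-item total is not the standard published score, which is why it should sit beside the five-item total and not replace it.

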9.3.6 Number and Length of Hospital Readmission for an Acute Complication of Cirrhosis

All occurrences of hospital admissions are collected via eCRF through Month 12 and will be listed.

For each subject, the number of hospital readmissions due to acute complication of cirrhosis will be counted. This endpoint will be presented by treatment as a continuous variable and analyzed by Poisson regression with adjustment for overdispersion using the Pearson statistic to estimate the scale parameter. The total number of hospital admissions in the SMT + Albutein 20% treatment group will be compared to the SMT alone. The response variable in the model will be the total number of hospital admissions experienced by a subject while on treatment. The model will include treatment group, IWRS stratification factors of region (Europe or North America) and history of hospitalization for acute decompensation of liver cirrhosis (yes or no) as factors. The logarithm of the subjects' treatment duration will be used as an offset variable in the model to adjust for subjects having different exposure times during which the events could occur. The estimated treatment effect (ie, the incidence rate ratio of SMT + Albutein 20% versus SMT alone) and corresponding 95% confidence interval (CI) will be presented.

Hospital readmissions occurring on treatment are defined as any hospital admission that occurred with a start date/time on or after the subjects treatment start date/time (treatment start date/time is defined as; date/time of randomization (for SMT alone group) or commencement of Albutein (SMT+ Albutein treatment group) treatment). If time is missing and the incidence occurred on or after the date of randomization (for SMT alone group) or the date of commencement of Albutein (for SMT+ Albutein treatment group) treatment it will be considered to have occurred while on treatment. If the hospital readmission is on-going at the end of the study, it is also considered as occurring on treatment.

Number	BIG-CL-SP-000319		
	Version	2.0	Status
Effective Date	09-Sep-2024	Page	37 of 52
Effective			
GRIFOLS			
Bioscience Industrial Group			

In the event a hospital readmission occurs prior to treatment start date and the discharge date is after the treatment start date it will be counted as an occurrence.

For each subject, the total duration (days) of hospital readmission for acute complication of cirrhosis will be calculated as the sum of the durations of each readmission (discharge date – admission date + 1) due to acute complication of cirrhosis. Descriptive statistics will be presented by treatment and analyzed by analysis of covariance (ANCOVA) with adjustment for stratification factors. If a subject's hospital readmission is considered on-going at the end of the study, the end of study completion date will be used to calculate the duration of the hospital readmission.

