4.4.1.2 Standard Medical Treatment

Subjects allocated to the control group will receive SMT, which will be administered per institution standards. Several guidelines are published for the management of decompensated cirrhosis (2-5). Diuretic therapy and dose modifications will be permitted on the basis of the evolution of ascites decompensation. Total paracentesis can be performed in the presence of tense ascites or symptoms due to the accumulation of abdominal fluid and will be followed by the administration of albumin. A TIPS will be considered when there are no other contraindications for this procedure for subjects with GI bleeding, refractory ascites, or hydrothorax. Complications such as bacterial infections, including SBP, or acute kidney injury, including type 1 HRS, will be treated according to current indications, which may require albumin infusion.

The usual treatment for comorbidities (ie, cardiac and respiratory diseases and diabetes) will be allowed according to the investigator's medical judgement. Any medication administered during the study (including any blood products) will be recorded in the electronic case report form (eCRF) as well as in the subject's medical record.

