5.4 Study Variables

5.4.1 Efficacy Variables

The following efficacy variables will be assessed in this study:

Primary efficacy

- Time to liver transplantation or death through 1 year after randomization

Secondary efficacy

- Time to liver transplantation or death through 3 and 6 months after randomization, and time to death through 3 and 6 months after randomization
- Time to death through 1 year after randomization
- Total number of paracenteses and incidence of refractory ascites according to the ICA criteria

Exploratory efficacy

- Incidence of ACLF (3, 6, and 12 months)
- Organ function sub-scores (liver, renal, cerebral, coagulation, circulation, and respiration), according to the CLIF-C OF score
- Number and length of hospital readmission for an acute complication of cirrhosis
- Number and length of ICU admission

GRIFOLS	Bioscience Industrial Group	Number	BIG-CL-SP-000319
		Version	2.0
IG1601 Statistical Analysis Plan		Status	Effective
		Effective Date	09-Sep-2024
		Page	17 of 52

Number	BIG-CL-SP-000319		
Version	2.0	Status	Effective
Effective Date	09-Sep-2024		
Page	18 of 52		

- Incidence of disease-related complications (anticipated disease progression includes, but not limited to HE, GI bleeding, portal hypertension, ascites, SBP, hyponatremia, and HRS)
- Serum albumin concentration and albumin functional capacity in serum (albumin binding capacity)
- Incidence of insertion of TIPS for refractory ascites
- CLIF-C ACLF score, CLIF-C AD score, MELD score, and Child-Pugh score
- Quality of life: EQ-5D-5L health questionnaire

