9.3.10 Incidence of Insertion of TIPS for Refractory Ascites

All occurrences of TIPS insertion are collected via a log through Month 12 and will be listed.

The number and percentage of subjects with at least one occurrence of TIPS insertion on or after treatment start date will be presented by treatment, and treatment differences will be analyzed using the same method as that for Incidence of disease-related complications. If a subject had at least one occurrence between screening and before the treatment start date it will be considered as a baseline occurrence. The odds ratio and corresponding 95% Confidence Interval (CI) will be determined from a logistic model, with the incidence of insertion of TIPS for Refractory Ascites (Yes/No) as the dependent variable and treatment, baseline occurrence, stratification factors of region (Europe or North America) as factors. Pre-hospitalization will not be included in the model as the subjects would be required to have been hospitalized to have an insertion of TIPS for refractory Ascites and this is considered as an exclusion criterion for the study.

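### SAP 9.3.6 gives the readmission model two different response variables: readmissions for an acute complication of cirrhosis, and all hospital admissions

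*SAP*

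**What the plan says.** **Readmissions.** The endpoint list in SAP 5.4.1 restricts the endpoint by cause: "Number and length of hospital readmission for an acute complication of cirrhosis". Protocol 7.1.3 and the heading of SAP 9.3.6 do the same. Section 9.3.6 then proceeds in this order:

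- The count: "For each subject, the number of hospital readmissions due to acute complication of cirrhosis will be counted".
- The link to the model: "This endpoint will be presented by treatment as a continuous variable and analyzed by Poisson regression with adjustment for overdispersion".
- The comparison: "The total number of hospital admissions in the SMT + Albutein 20% treatment group will be compared to the SMT alone".
- The response variable: "The response variable in the model will be the total number of hospital admissions experienced by a subject while on treatment".
- The on-treatment rule: "Hospital readmissions occurring on treatment are defined as any hospital admission that occurred with a start date/time on or after" the start of treatment.
- The length analysis: total days are summed over readmissions for an acute complication of cirrhosis only, and analysed by ANCOVA.

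The section also says that every hospital admission is collected on the eCRF through Month 12 and will be listed.

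**TIPS.** SAP 9.3.10 is headed as TIPS inserted for refractory ascites. Its table counts "subjects with at least one occurrence of TIPS insertion on or after treatment start date", and an insertion between screening and treatment start is a baseline occurrence. Neither rule states an indication. The logistic model's dependent variable is named as TIPS for refractory ascites. Protocol 4.4.1.2 allows TIPS to be considered "for subjects with GI bleeding, refractory ascites, or hydrothorax".

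**The concern.** The response-variable sentence is the one a programmer implements, and it carries no cause restriction. Because the eCRF collects all admissions, nothing upstream removes the others. Protocol 8.3.7 itself foresees stays unrelated to worsening cirrhosis, such as elective, pre-planned and social ones. Followed literally, the number and the length of one named endpoint would describe different sets of events.

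Two programmers could each follow 9.3.6 faithfully and report different rate ratios under the same title. The trial is open-label (Protocol 4.3.3), so a choice left open in the SAP may be made after admissions by arm are visible. SAP section 2 says that the planned analyses are meant for regulatory submissions and manuscripts, so the label on the estimate matters even for an exploratory endpoint.

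For TIPS the stake is smaller: the table could count procedures done for bleeding or hydrothorax beside a model that is meant to exclude them.

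**Working it through.** The documents state no event rate, event count or power for either endpoint, so there is no figure to reproduce. The check is a comparison of texts, followed by an illustration on assumed values.

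**Step 1. Each statement on readmissions, by cause restriction**

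| Statement | Restricted to acute complications of cirrhosis? |
|---|---|
| Endpoint list, SAP 5.4.1 | Yes |
| Heading, SAP 9.3.6 | Yes |
| Count per subject | Yes |
| Link from count to Poisson model | Yes, because it refers back to that count |
| Comparison of arms | No |
| Response variable | No |
| On-treatment rule | No, but mainly a timing rule |
| Length analysis | Yes |

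The link sentence and the response-variable sentence define the same model differently. Both cannot be implemented.

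**Step 2. What the unrestricted reading would do to the estimate**

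Let *f* be the share of control-arm admissions that are cirrhosis-related and *RR* the true rate ratio for those admissions. Assume that treatment does not change the rate of other admissions. With a control-arm total rate of 1, the control arm has *f* + (1 − *f*) and the Albutein arm has *f* × *RR* + (1 − *f*). Ignoring differences between strata,

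all-cause ratio = *f* × *RR* + (1 − *f*).

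For *RR* = 0.70:

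- *f* = 0.90: 0.63 + 0.10 = 0.73
- *f* = 0.70: 0.49 + 0.30 = 0.79
- *f* = 0.50: 0.35 + 0.50 = 0.85

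Over a wider range of assumed values:

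| True *RR* | *f* = 90% | *f* = 70% | *f* = 50% |
|---|---|---|---|
| 0.60 | 0.64 | 0.72 | 0.80 |
| 0.70 | 0.73 | 0.79 | 0.85 |
| 0.80 | 0.82 | 0.86 | 0.90 |

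Every *f* and *RR* here is an assumption. Under this model the all-cause ratio always lies between the true ratio and 1.

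**Step 3. TIPS**

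| Statement in SAP 9.3.10 | Restricted to refractory ascites? |
|---|---|
| Heading | Yes |
| Number and percentage of subjects | No |
| Baseline occurrence | No |
| Dependent variable of the logistic model | Yes |

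The model that estimates the odds ratio names the stated endpoint. The mismatch is confined to the descriptive count and the baseline rule, although the baseline occurrence is also a factor in the model. No size is calculated, because the model's outcome is already restricted.

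**The case against.** The strongest reply is that 9.3.6 should be read as a whole. The heading, the count and the link sentence establish a cause-specific endpoint, and the later mention of total admissions is shorthand for it. The on-treatment sentence says when an admission counts, not why it occurred. SAP section 12, which lists changes from the planned analysis, announces no move to all-cause admissions, and the SAP revision history describes the edit to 9.3.6 as clarification. All admissions will be listed, so either reading could be checked afterwards.

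Much of this stands. It makes the cause-specific reading the likelier intention, and a reader who infers that the plan is simply all-cause goes further than the text. It does not remove the conflict: the sentence that defines the model's response still says something else, and the plan should not depend on the programmer choosing the charitable reading.

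Three stronger inferences are tempting and unsupported:

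- *Neither comparison measures its stated endpoint.* This is wrong for TIPS, where the dependent variable is the stated endpoint, and unproven for readmissions, where the text points both ways.
- *The effect could reverse.* With other admissions unaffected, the ratio moves only toward 1. A reversal would need other admissions to rise on Albutein, and the documents give no rate for that. Nor would infusion-related stays necessarily be confined to one arm: Protocol 4.4.1.2 provides for albumin after paracentesis and for some complications under standard treatment.
- *The TIPS indication is not recorded.* The visit lists mention only an assessment of insertion, but SAP 9.3.10 says insertions are collected on a log, and the fields of that log are not in the documents.

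**Conclusion.** The point holds as an internal contradiction. SAP 9.3.6 specifies two response variables for one model, and the more explicit of the two does not match the stated endpoint or the length analysis. If it were followed literally, the likely consequence is dilution: a true ratio of 0.70 would appear between 0.73 and 0.85 for cirrhosis shares from 90% down to 50%. That range rests on assumed shares and on no treatment effect on other admissions.

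The length half of the endpoint is correctly restricted. The TIPS part is a smaller mismatch between a descriptive count, a baseline rule and a correctly named model outcome.

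Both endpoints are exploratory and outside the fixed testing sequence in SAP 6.5, so no primary or secondary conclusion depends on them.

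**What to change.** In SAP 9.3.6, write readmissions due to an acute complication of cirrhosis in the comparison, response-variable and on-treatment sentences. State that the model uses the same events as the length analysis. Report all-cause admissions as a separate row, labelled as such.

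In SAP 9.3.10, add the refractory-ascites restriction to the number-and-percentage rule and to the baseline-occurrence rule, so that both match the model. State how the indication is identified, query the source only where it is missing, and list TIPS inserted for other reasons separately.

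The cost is a few SAP sentences. The readmission edit should need no new data: all admissions are collected, and the existing count and length analysis already require each one to be classified by cause. The TIPS edit needs queries only if the log does not hold the indication.
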